- Laboratory evidence, which may include pulmonary congestion on chest x-ray, elevated natriuretic peptide level, worsening oxygenation or respiratory acidosis.

Examples of intravenous heart failure therapy would include:

- IV bolus or infusion of loop diuretics, vasodilators such as nitrates, nitroprusside, nesiritide, vasopressors including dobutamine or dopamine, and inotropic agents such as milrinone.
- Also included would be other invasive or mechanical heart failure treatments such as ultrafiltration, or hemodynamic assist devices such as intra-aortic balloon pumps or LVADs.

Notes:

1. Treatment with IV antiarrhythmic medication, electrical cardioversion and/or ablation in the absence of other intravenous or invasive heart failure treatments would **not** *per se* constitute an ADHF event.
2. Heart failure exacerbation that can be managed solely by augmentation of oral heart failure therapies does not meet criteria for heart failure hospitalization.
3. ADHF that develops secondary to another diagnosis such as a non-cardiac diagnosis (e.g., pneumonia/bronchitis, limb fracture, renal failure), an acute MI complicated by ADHF, acute onset of atrial fibrillation with rapid ventricular response or a rupture chordae would **not** be counted as ADHF events.

HEART TRANSPLANT

Replacement of a native heart with a donor heart.

HEMATOMA

A swelling or mass of blood (usually clot), six (6) centimeters or longer, that causes bruising or bleeding of the body tissue at the catheter insertion site. This event may occur after the index procedure and may or may not require treatment.

HEMOLYSIS

A new onset of anemia associated with laboratory evidence of red cell destruction. This is diagnosed as plasma free hemoglobin that is greater than 40 mg/dL on two (2) measures within 24 hours or on one measure if the intervention is initiated based upon other clinical symptoms.

HYPOTENSION/HYPERTENSION

Hypotension

A decrease of the systolic and diastolic blood pressure to below normal for the subject, which requires treatment. This may occur as a result of infection, fever, hemorrhage, shock, or anemia. It may occur anytime throughout a subject's participation in the study.

Hypertension

A higher than normal blood pressure that requires treatment. This may occur at any time throughout a subject's participation in the study.

INDEX PROCEDURE

The index procedure takes place immediately following randomization and is the starting point for timing of all follow-up evaluations and data analyses.

INFECTION, GENERALIZED

The presence and growth of microorganisms that produces tissue damage, usually accompanied by inflammation. Infection requiring treatment will be documented as an adverse event.

INFECTION AT THE CATHETER INSERTION SITES

An infection or inflammatory response that occurs at one or more catheter insertion sites in relationship to the index procedure and that requires treatment.

INFORMED CONSENT

Informed consent is a process by which a subject voluntarily confirms his or her willingness to participate in a particular study, after having been informed of all aspects of the investigation that are relevant to the subject's decision to participate. Informed consent is documented by means of a written, signed, and dated informed consent form.

INVESTIGATOR

A person responsible for the conduct of the clinical investigation at an investigation site. If an investigation is conducted by a team of individuals at an investigation site, the Investigator is the responsible leader of the team and may be called the Principal Investigator. The Investigator is responsible for assuring the investigation is conducted in accordance with all applicable regulations including those protecting human subjects.

INVESTIGATIONAL PRODUCT

Investigational product is defined as the investigational device, its accessories, and accompanying labeling.

LEFT VENTRICULAR EJECTION FRACTION

The percentage of the blood emptied from the ventricle during systole.

LEUKOPENIA

Decrease in white blood count to below the lower limit of normal. Leukopenia may be caused by prolonged radiation exposure.

MAJOR ADVERSE EVENT (MAE)

Defined as one of the following: (1) Death; (2) Myocardial Infarction; (3) Device embolization; (4) Vessel erosion requiring percutaneous or surgical intervention; (5) Cardiac perforation requiring percutaneous or surgical intervention; or (6) Occurrence of cardiac surgery or percutaneous coronary intervention associated with device failure.

MARKER CATHETER

An angiographic catheter used to measure the coronary sinus/great cardiac vein.

MEDICAL ETHICS COMMITTEE

The medical ethics committee, according to Directive 2001/20/EC, is an independent body in a member state of the European Union, consisting of healthcare professionals and non-medical members, whose responsibility it is to protect the rights, safety and well being of human subjects involved in a clinical trial and to provide public assurance of that protection, by, among other things, expressing an opinion on the clinical trial protocol, the suitability of the investigators involved in the trial and the adequacy of facilities, and on the methods and documents to be used to inform trial subjects and obtain their informed consent.

MITRAL ANNULOPLASTY RING

A prosthetic ring sutured into the mitral valve annulus during open heart surgery.

MITRAL REGURGITATION

The backward flow of blood across the mitral valve from the left ventricle to the left atrium that results from imperfect closure of the mitral valve. Mitral valve regurgitation may be classified in several ways including echocardiographically, fluoroscopically, and clinically.

Primary cardiomyopathy with secondary mitral regurgitation will be distinguished by the presence of left ventricular dilation, left ventricular dysfunction, and 2+ - 4+ mitral regurgitation and the absence of significant mitral valve pathology where mitral valve pathology includes mitral valve prolapse, flail leaflet, or evidence of degenerative or rheumatic mitral valve disease. Primary mitral regurgitation with secondary dysfunction implies that structural valve pathology exists (e.g., prolapse, flail leaflet, degenerative or rheumatic mitral valve disease) and has caused the left ventricular dilation and dysfunction. Thus, subjects with significant organic mitral valve pathology and left ventricular dysfunction will be considered to have primary mitral regurgitation and secondary dysfunction.

Mitral regurgitation may occur at any time throughout a subject's participation in the study. An acute, hemodynamically significant increase in MR will be documented as an adverse event.

MITRAL STENOSIS

A narrowing of the mitral orifice, obstructing free flow of blood from the left atrium to the left ventricle. This may occur at any time throughout a subject's participation in the study.

This study will define mitral stenosis as being present if both of the following criteria are met:

1. Either peak E wave velocity > 1.5 m/s (corresponding to a peak gradient \geq 10 mmHg), or mean pressure gradient > 5 mmHg, and
2. Either, one of the following:
 - a. Mitral valve area calculated by PHT is < 2.0 cm² (i.e., PHT > 110 msec), or
 - b. 2D mitral valve planimetry (or alternatively a mitral inflow color PISA, if present) reveals a mitral valve area of < 2.0 cm².

MITRAL VALVE

The cardiac valve between the left atrium and left ventricle.

MITRAL VALVE INJURY

Injury or trauma to the mitral valve that requires observation or intervention throughout a subject's participation in the study.

MYOCARDIAL INFARCTION

Myocardial infarction (MI) is defined for events that occur \leq 24 hours and for events that occur > 24 hours after the index procedure or any percutaneous cardiac intervention that may be required during the subject's participation in the study.

Less than or equal to 24 hours post-intervention

In patients undergoing PCI with normal ($\leq 99^{\text{th}}$ percentile URL) baseline cTn concentrations, elevations of cTn $> 5 \times 99^{\text{th}}$ percentile URL occurring within 48 hours of the procedure—plus either:

- (i) evidence of prolonged ischemia (≥ 20 min) as demonstrated by prolonged chest pain, or
- (ii) ischemic ST changes or new pathological Q waves, or
- (iii) angiographic evidence of a flow limiting complication, such as of loss of patency of a side branch, persistent slow-flow or no-reflow, embolization, or
- (iv) imaging evidence of new loss of viable myocardium or new regional wall motion abnormality

is^[SEP] defined as PCI-related MI (type 4a).

Note: When a cTn value is $\leq 5 \times 99^{\text{th}}$ percentile URL after PCI and the cTn value was normal before the PCI—or when the cTn value is $> 5 \times 99^{\text{th}}$ percentile URL in the absence of ischemic, angiographic or imaging findings—the term ‘myocardial injury’ should be used.

More than 24 hours post-intervention

Myocardial infarctions more than 24 hours after percutaneous cardiac intervention will be defined according to the ESC/ACCF/AHA/WHF Expert Consensus Universal Definition of MI³⁷ and will be adjudicated by an independent Clinical Events Committee.

MYOCARDIAL ISCHEMIA

Inadequate circulation of blood to the heart muscle due to obstructions of coronary arteries as documented by electrocardiography and/or imaging modalities. This may occur at any time throughout a subject’s participation in the study.

NAUSEA/VOMITING

Nausea is an uneasiness of the stomach that often accompanies the urge to vomit, but doesn’t always lead to vomiting. Vomiting is the forcible voluntary or involuntary emptying (“throwing up”) of stomach contents through the mouth. Nausea or vomiting requiring treatment will be documented as adverse events.

NEW YORK HEART ASSOCIATION CLASSIFICATION (NYHA)

Classification system for defining cardiac disease and related functional limitations into four broad categorizations. NYHA Classification assessment will be made by independent examiner at all study time-points. Refer to Appendix D for specific definitions.

NITINOL

A super-elastic shape-memory Nickel-Titanium alloy used commonly in cardiac, dental, and orthopedic implants as well as in other non-implant medical devices.

NON-PYROGENIC

The term applies to a biocompatibility test of the device materials to assure that no foreign proteins are produced by the interaction of the device with the myocardial tissue that would cause a fever.

PAIN

An unpleasant sensory and emotional experience arising from actual or potential tissue damage, which requires treatment.

PERFORATION (arterial, venous or cardiac)

Perforation associated with puncture and/or rupture of a cardiac structure, or of a arterial or venous access vessel.

A perforation during the index procedure will be classified as a major adverse event only if it is associated with puncture or rupture of a cardiac structure (heart, coronary artery, and/or coronary vein) leading to hemopericardium and requiring percutaneous or surgical intervention.

PERFUSION

Passage of blood into the surrounding tissue

PERICARDIAL EFFUSION

Fluid in the pericardial space documented by echocardiography or other methods.

PERICARDITIS

Inflammation of the pericardium or development of an unexplained pericardial effusion. Pericarditis will be diagnosed by the presence of at least two of the following clinical features: 1) chest pain, 2) pericardial friction rub on exam, 3) characteristic ECG changes (new widespread ST elevation or PR depression), and 4) pericardial effusion.

PERIPHERAL ISCHEMIA

Inadequate flow of blood to the arteries or veins of the extremities that may result in pain or injury to the blood vessel. This event may or may not require intervention and can occur at any time throughout a subject's participation in the study.

PHARYNGEAL / LARYNGEAL TRAUMA

Injury to the pharynx or larynx (e.g., dysphagia, vocal cord disorder, throat pain), which requires treatment and is related to a transesophageal echocardiogram performed during the subject's participation in the study.

PHYSICAL INJURY

Trauma or damage to a part of the body, which requires treatment and is related to functional tests (e.g., exercise treadmill) performed during the subject's participation in the study.

PLICATION

The creation of folds or tucks in tissue (e.g., vein) to shorten its length.

PNEUMONIA

An inflammation of the alveoli, interstitial tissue, and bronchioles of the lungs due to infection by bacteria, virus, or other pathogenic organisms, or to irritation by chemical or other agents.

PNEUMOTHORAX

A collection of air in the pleural cavity that requires intervention. This may be a result of injury, bleb, or superficial lung abscess and may occur at any time throughout a subject's participation in the study.

RADIATION DERMATITIS

Skin burns ranging from erythema to blistering/ulceration, and caused by prolonged radiation exposure.

RECAPTURE

The mechanism of retrieving the CARILLON implant from its anchored position within the coronary sinus/great cardiac vein. This is achieved by using the delivery catheter to collapse the device into the catheter for removal from the subject. The CARILLON Mitral Contour System is designed to enable acute recapturing (i.e., prior to decoupling from the delivery system) if the implant cannot be placed safely in its intended location.

REINTERVENTION

Any unscheduled visit to the operating room or catheterization laboratory for reintervention related to the CARILLON investigational procedure or study device.

RENAL FAILURE

Renal insufficiency resulting in an increase in serum creatinine that requires dialysis. This event may occur as a result of any study procedures that require the use of contrast media.

RENAL INSUFFICIENCY

Any clinically significant increase in creatinine above baseline requiring treatment (excluding dialysis).

RESPIRATORY DISTRESS

Severe and sustained impairment of respiratory function, which is related to study procedures and requires treatment.

SEPTICEMIA/SEPSIS

A serious, systemic, rapidly progressive, life-threatening infection caused by pathogenic organisms or their toxins, that may or may not be associated with a positive blood culture, and requiring hospitalization and treatment with antibiotics. A full course of antibiotic therapy is defined as seven (7) days or longer.

SERIOUS ADVERSE EVENT

Adverse event that

- a) led to death,
- b) led to serious deterioration in the health of the subject, that either resulted in
 - 1) a life-threatening illness or injury, or
 - 2) a permanent impairment of a body structure or a body function, or
 - 3) in-patient or prolonged hospitalization, or

- 4) medical or surgical intervention to prevent life-threatening illness or injury or permanent impairment to a body structure or a body function,
c) led to foetal distress, foetal death or a congenital abnormality or birth defect

NOTE Planned hospitalization for a pre-existing condition, or a procedure required by the CIP, without serious deterioration in health, is not considered a serious adverse event.

SIGNIFICANT ORGANIC MITRAL VALVE PATHOLOGY

Moderate or severe myxomatous degeneration, with or without mitral leaflet prolapse, rheumatic disease, full or partial chordal rupture.

STROKE

A neurological deficit lasting 24 hours or longer, or lasting less than 24 hours with a brain imaging study showing infarction. This may occur at any time throughout a subject's participation in the study and may or may not require treatment.

SYSTOLIC ANTERIOR MOTION

Anterior displacement of the anterior mitral valve leaflet during systole causing left ventricular outflow tract obstruction.

TENSIONING

With the CARILLON implant deployed, tensioning is the process of applying translational movement (by pulling) of the delivery system to cause the coronary sinus/great cardiac vein tissue to plicate.

TIMI CLASSIFICATION

Thrombolysis in Myocardial Infarction has four classifications:

TIMI 0: No perfusion.

TIMI 1: Penetration with minimal perfusion. Contrast fails to opacify the entire bed distal to the stenosis for the duration of the cine run.

TIMI 2: Partial perfusion. Contrast opacifies the entire coronary bed distal to the stenosis. However, the rate of entry and/or clearance is slower in the coronary bed distal to the obstruction than in comparable areas not perfused by the dilated vessel.

TIMI 3: Complete perfusion. Filling and clearance of contrast equally rapid in the coronary bed distal to stenosis as in other coronary beds.

TISSUE NECROSIS

Tissue death within the external or internal layers of the blood vessel(s) (arterial or venous), heart structures, or myocardium caused by the CARILLON implant, which requires treatment. This may occur at any time throughout a subject's participation in the study.

TISSUE PENETRATION

Outward radial movement of the CARILLON implant (e.g., the anchor wireforms) from the lumen of the vein into the adjacent tissue, with no compromise to the

integrity of the tissue. The relative position of the device with respect to its intended position within the vein is unchanged.

TRANSIENT ISCHEMIC ATTACK (TIA)

A neurological deficit lasting less than 24 hours and, if an imaging study is performed, shows no evidence of infarction. This may occur at any time throughout a subject's participation in the study and may or may not require treatment.

UNANTICIPATED SERIOUS ADVERSE DEVICE EFFECT (USADE)

Serious adverse device effect which by its nature, incidence, severity or outcome has not been identified in the current version of the study documentation.

URINARY TRACT INFECTION

Infection of the urinary tract with microorganisms, which requires treatment.

VASOVAGAL REACTION

Hypotension, pallor, sweating, hyperventilation, bradycardia, and/or syncope produced by stimulation of the vagus nerve during study-related procedures. A vasovagal reaction requiring treatment will be documented as an adverse event.

VENOGRAM

Angiography of the vein.

VENTRICULAR ASSIST DEVICE

A mechanical pump that assists the heart by pumping blood through the body.

VESSEL EROSION

A physical or inflammatory process adjacent to the CARILLON implant causing loss of tissue integrity of the blood vessels (arterial or venous), heart structures, or myocardium. Vessel erosion will be classified as a major adverse event only if percutaneous or surgical intervention is required.

VESSEL OCCLUSION (arterial or venous)

Complete blockage of a blood vessel preventing the flow of blood and resulting in cardiac symptoms and requiring treatment.

VESSEL SPASM OR STENOSIS (ARTERIAL OR VENOUS)

Vessel Spasm

Temporary abrupt contraction of the muscles in the wall of a blood vessel resulting in reduced blood flow. A spasm that results in myocardial ischemia or requiring treatment will be considered an adverse event.

Vessel Stenosis

Narrowing of a blood vessel that requires treatment.

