3.2.2.1 Safety

The following secondary safety endpoints will measure the effect of the CARILLON Mitral Contour System on clinical safety parameters of interest, relative to the Control population

- To document the difference in the rate of major adverse events between randomized groups, at 1 and 12-months post randomization.

Major Adverse Events are defined as a composite of the following:

- Death
- Myocardial Infarction
- Device Embolization
- Vessel Erosion, requiring percutaneous or surgical intervention
- Cardiac Perforation, requiring percutaneous or surgical intervention
- Occurrence of cardiac surgery or percutaneous coronary intervention associated with device failure

- To assess the rate of heart failure hospitalizations (number of admissions, and total associated days in the hospital), from the time of the index procedure through twelve months of follow-up.

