3.5.3.3 Eligibility Venogram

A coronary sinus venogram will be performed immediately prior to randomization in order to assess eligibility for the study (Inclusion Criteria #5).

If the study subject does not meet the final venogram eligibility criteria, the subject is an enrolled screen failure. Randomization does not occur and the subject is followed through discharge only.

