3.7.1.2 Treatment Group

For subjects randomized to the Treatment group, the CARILLON Mitral Contour System procedure will be performed. The implant procedure is described in Appendix A: Instructions For Use.

Pre-medication will be according to institutional procedures for cardiac catheterization. Additionally, subjects will be heparinized prior to the angiographic procedure according to institutional policies. Anti-platelet therapy is not required in the REDUCE FMR Trial, however, individual Investigators may prescribe such medications in accordance with their institution's standard of care or as necessary to treat other concurrent cardiac conditions. The use of anti-platelet therapy will be noted on the case report forms.

Either Transesophageal Echocardiogram (TEE) or Transthoracic Echocardiogram (TTE) may be used during the implant procedure to evaluate the safety and effectiveness of device placement. If TEE is used during the index procedure, the assessment of the left atrial appendage clot exclusion criteria (required for subjects with existing atrial

fibrillation) may be made immediately prior to randomization and the index procedure (i.e., a separate TEE is not required.)

All subjects randomized to the Treatment group will have coronary angiography performed prior to the CARILLON implant attempt. This is in order to establish the baseline flow characteristics of the coronary arterial vessels in the same location (AV groove) as the coronary sinus/great cardiac vein. If coronary artery flow compromise is noted during the CARILLON implant procedure, the CARILLON device can be recaptured. At the investigator and proctor's discretion, another CARILLON device attempt can occur if the device can be placed in a portion of the coronary sinus/great cardiac vein where coronary flow is not compromised.

However, if there is **clinically significant** coronary artery compromise, mitral stenosis, systolic anterior motion or other safety issues, the CARILLON implant will be recaptured and the procedure ended.

If the patient becomes hemodynamically unstable and/or no CARILLON device implant is attempted, the subject will be classified as a Procedural Screen Failure in the Treatment group and will be followed through 1-month with a safety assessment only (full 1-month follow-up assessments are not necessary), then exited from the study.

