5.1.8 Clinical Events Committee

A Clinical Events Committee (CEC) will be responsible for adjudicating MAEs, and device (incl. USADEs) and procedural adverse events. The CEC members will be independent medical professionals with expertise in the fields of cardiology, interventional cardiology (including cardiac surgery), or heart failure and without conflict of interest. The CEC will adjudicate to determine if the event is:

- considered a major adverse event
- related to the device (implant and/or catheter)
- related to the procedure
- an anticipated or unanticipated adverse event.

In addition, the CEC will adjudicate events resulting in death to determine whether the death is considered cardiac, non-cardiac, or operative mortality. Members will be provided event data from the clinical study without site or Investigator identification.

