An opening or hole through the esophagus, requiring treatment. This may be related to the transesophageal echocardiogram (TEE) performed during the index procedure or anytime during the trial should this test become necessary.

Esophageal stricture

An abnormal narrowing of the esophagus acquired from trauma (e.g., TEE) or infection that may result in mechanical or chemical irritation, muscular spasm, or pressure from adjacent structure or tumors, and which requires treatment. This event may occur at any time throughout a subject's participation in the study and may be temporary or permanent.

FATIGUE

A feeling of tiredness or weariness resulting from continued activity or as a side effect of prolonged radiation exposure or psychotropic drug.

FEVER

A fever above 101 degrees Fahrenheit that results in medical intervention. This may occur at any time throughout a subject's participation in the study.

GREAT CARDIAC VEIN

The vein in the transverse groove between the left cardiac atrium and ventricle that drains into the coronary sinus.

HEADACHE

An acute or chronic, diffuse pain in different portions of the head, not confined to any nerve distribution area. It may be frontal, temporal, or occipital, and may be confined either to one side of the head or to the region immediately over one eye. Headaches requiring treatment will be documented as adverse events.

HEART FAILURE

A chronic syndrome resulting from failure of the heart to maintain adequate circulation of blood. Symptoms resulting from decompensation of the heart or exacerbation of heart failure symptoms, which occur during the study and require treatment, will be documented as adverse events.

HEART FAILURE HOSPITALIZATION

A diagnosis of acute decompensated heart failure hospitalization (ADHF) requires an in-hospital stay that includes at least one calendar date change and requires intravenous or mechanical heart failure treatment. The length of hospital stay will be calculated from admission to discharge to home or other disposition.

The diagnosis of ADHF will be based on:

- Symptoms of worsening heart failure such as increased shortness of breath, orthopnea, paroxysmal nocturnal dyspnea, fatigue, decreased exercise tolerance or history of weight gain;
- Physical examination evidence such as neck vein distention, the presence of a third heart sound, bilateral pulmonary rales, worsening ascites or pedal edema, hypotension or signs of worsening end-organ perfusion; and/or

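### The HF-hospitalization endpoint leaves out decompensation secondary to another diagnosis, with no exception when the device or procedure caused that diagnosis, so the comparison can lean towards the device

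*Protocol*

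**What the plan says.** Protocol 3.2.2.1 places HF hospitalization among the secondary safety endpoints: "To assess the rate of heart failure hospitalizations (number of admissions, and total associated days in the hospital"), counted from the index procedure to 12 months and set against Control. SAP 2.4.3.1 repeats the endpoint without redefining it, and SAP 2.3.1 takes the data from the Clinical Events Committee (CEC) database.

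Protocol 9.2 defines the event. It needs an "in-hospital stay that includes at least one calendar date change and requires intravenous or mechanical heart failure treatment". Note 3 then takes out "ADHF that develops secondary to another diagnosis such as a non-cardiac diagnosis (e.g., pneumonia/bronchitis, limb fracture, renal failure), an acute MI complicated by ADHF", and goes on to "acute onset of atrial fibrillation with rapid ventricular response or a rupture chordae would", ending with the statement that these do not count as acute decompensated HF (ADHF) events. The words introducing the list leave it open, and nothing in it depends on what caused the other diagnosis.

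The protocol itself recognises device or procedure routes to some of these diagnoses. On renal failure, 9.2 says: "This event may occur as a result of any study procedures that require the use of contrast media". On the implant, 3.7.1.2 says: "If coronary artery flow compromise is noted during the CARILLON implant procedure, the CARILLON device can be recaptured". Table 5.1 lists myocardial infarction (MI), renal failure, arrhythmias and mitral valve injury as anticipated events. That table also covers catheterization and background heart failure, so it does not attribute each of them to the device.

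**The concern.** Leaving out decompensation triggered by an unrelated illness is reasonable, and randomization balances such illness between the arms in expectation. It does not balance a trigger that the implant attempt creates. Suppose an implant causes an infarct and the patient is then treated intravenously for heart failure in hospital. Under Note 3 that patient adds no HF admission and no hospital days to the Treatment arm. A safety endpoint compared with Control would normally be expected to show harm that runs through a complication of the device. At stake is whether the reported HF admissions and days understate what happened in the Treatment arm.

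**Working it through.** **Stated figure.** There is none to reproduce. Neither document gives a rate, margin or power for HF hospitalization, and Protocol 6.8 reports the secondary endpoints descriptively. The check is therefore to follow each kind of admission through the rules and then to set a scale.

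**Routes, each ending in an IV-treated HF stay across a calendar date:**

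| Route | HF admissions and days | Where else it appears |
|---|---|---|
| Device or procedure leads to decompensation with no other diagnosis between | Counted | AE, SAE and relatedness tables |
| Device leads to acute MI, then decompensation | Not counted | MI as a major adverse event (MAE); AE, SAE and relatedness tables |
| Study contrast leads to renal failure, then decompensation | Not counted | AE, SAE and relatedness tables; renal failure is not an MAE component |
| Procedure leads to rapid AF of acute onset, or to chordal rupture, then decompensation | Not counted | AE, SAE and relatedness tables; neither is named as an MAE component |
| Background pneumonia or MI in either arm, then decompensation | Not counted | AE and SAE tables; MI also as MAE |

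**Direction.** Let b be the proportion of patients whose HF admission Note 3 removes for reasons common to both arms, and d the further proportion removed in Treatment because of the implant attempt.

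- Removed in Treatment: b + d. Removed in Control: b.
- Counted difference (Treatment minus Control) = true difference − (b + d) + b = true difference − d.

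The shared part cancels in expectation. What remains lowers the Treatment figure.

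**Scale.** Planned randomization is 120 patients at 3:1 (Protocol 3.6 and 6.7).

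- Treatment: 120 × 3/4 = 90. Control: 120 × 1/4 = 30.
- One Treatment patient: 1/90 = 1.1 percentage points.

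The SAP's intent-to-treat set leaves out patients whose procedure stopped before an implant attempt, so the working denominator may be slightly below 90.

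**Illustration, on assumptions only.** Suppose the true proportion p with an HF admission is the same in both arms, between 20% and 40%. Suppose also that b = 0, and that a share d of Treatment patients lose their only HF admission through Note 3. The apparent relative risk is (p − d)/p, where the truth is 1.0.

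- d = 1/90 (one patient): 1 − 0.0111/0.20 = 0.94 to 1 − 0.0111/0.40 = 0.97.
- d = 2% (90 × 0.02 = 1.8 patients): 0.18/0.20 = 0.90 to 0.38/0.40 = 0.95.
- d = 5% (90 × 0.05 = 4.5 patients): 0.15/0.20 = 0.75 to 0.35/0.40 = 0.88.

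The documents support no particular value of p or d. The lines show only how the comparison responds. No figure can be given for total days, where a single long stay could weigh more than one admission does in the count.

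**The case against.** The case on the other side is substantial.

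- **Captured elsewhere.** A reader might infer that these admissions vanish from the safety assessment. They do not. MI is an MAE component. Treated worsening of heart failure is an adverse event (Protocol 9.2), and hospitalization with serious deterioration makes it serious (5.1.1.5). SAP 2.4.4 compares adverse events, serious adverse events and CEC-adjudicated device- and procedure-related events between arms, and itself calls these secondary safety endpoints. SAP 2.4.5 adds serious adverse events through 6 and 12 months.
- **Contrast is not confined to Treatment.** Protocol 3.5.3.3 says: "A coronary sinus venogram will be performed immediately prior to randomization in order to assess eligibility for the study". Controls also have angiography unless a recent arteriogram is accepted.
- **Weak evidence of mechanism.** In AMADEUS, TITAN and TITAN II, coronary compromise is given as a reason why some patients did not receive a device. That does not document an infarct followed by an HF admission.
- **Low decision weight.** The endpoint is descriptive, with no success rule. Restricting it to primary decompensation is a legitimate design choice.

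All of this stands, and it limits the point. It does not remove it. SAP 2.4.4 gives numbers of events and patients, not HF admissions and hospital days, which are what this endpoint measures. The anticipated-event term for HF hospitalization takes its meaning from the same Section 9.2 definition, so it does not recover the excluded stays either. Contrast exposure overlaps but is not equal: every Treatment patient has coronary angiography, a Control may not, and only Treatment patients have an implant attempt.

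**Conclusion.** The point holds in limited form. Followed as written, Note 3 can undercount HF admissions and days that reach the patient through a device- or procedure-caused diagnosis. Any excess from the implant attempt lies in Treatment only, and no planned analysis restores those admissions or days. The direction follows from the text; the size does not. It is probably small, at about 1.1 percentage points of 90 for each Treatment patient affected.

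Three stronger readings are not supported:

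- **That all HF admissions caused by the device are excluded.** Only those running through another diagnosis are. Nothing excludes an admission for being device-related.
- **That any new atrial fibrillation or arrhythmia triggers the exclusion by name.** The text names only AF of acute onset with a rapid ventricular response.
- **That the 30-day MAE rates of the earlier studies (13%, 1.9% and 2.8%) give the number lost.** MI is the only MAE component that Note 3 names, its share of those rates is not stated, and renal failure and AF are not MAE components at all.

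**What to change.** In SAP 2.4.3.1, next to the analysis under the Note 3 definition, prespecify two additions:

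1. By arm, all HF admissions with intravenous or mechanical HF treatment and at least one calendar date change, and their total days, whatever the precipitant.
2. A listing by arm of the admissions that Note 3 removed, with the precipitating diagnosis and the CEC's finding on whether it was "related to the device (implant and/or catheter") or to the procedure.

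The first treats both arms alike and shows directly whether the exclusion changes the comparison. It is safer than rewriting Note 3 to count only precipitants judged possibly device-related. The protocol's middle causality category (5.1.4) also admits events that the patient's own condition could explain. A late background infarct could then count in an implanted patient, while the same infarct in a Control could not be related to the implant.

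The cost is one more table and a short listing. The CEC already adjudicates device and procedure relatedness, and its database already feeds this endpoint. The sponsor should confirm that the database keeps the excluded admissions with their dates and treatment. The Treatment HF figure may look slightly less favourable.
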